6.3 Dose Modifications and Reductions

Doses of ARRY-382 and pembrolizumab may be modified throughout the study.

Cycle 1 Day 1 is defined as the first day of study drug treatment with both ARRY-382 and pembrolizumab. Per the schedule of events, cycles are defined as 21 days and pembrolizumab should be administered Q3W. In the event of temporary dose interruptions, the re-start of subsequent cycles may correspond with administration of either ARRY-382 or pembrolizumab. Doses of ARRY-382 withheld during a cycle will not be made up.

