- c. All prior cancer treatments are to be recorded; other prior treatments (i.e., other than cancer treatments) taken within 4 weeks of screening should also be recorded.
- d. These assessments do not need to be repeated if they were performed within 96 hours of Cycle 1 Day 1. For the triplicate 12-lead ECG, the predose assessment need not be repeated if it was performed within 96 hours of Cycle 1 Day 1, but the assessment at 4 hours postdose must be performed regardless of when the predose assessment was performed.
- e. Physical examination includes height at screening only.
- f. Vital signs include blood pressure, pulse, and temperature.
- g. For females of childbearing potential only (see [Section 7.1.2](#)), serum pregnancy tests are to be performed at screening; serum or urine pregnancy tests will be allowed at subsequent time points.
- h. All patients are to have a fresh biopsy plus a blood sample obtained at screening, or submit archived tumor samples from the most recent sample available plus a blood sample. The requirement of tumor tissue may be waived only with Sponsor approval (see [Section 7.1.5](#)).
- i. Three 12-lead ECGs are to be performed over a period of approximately 5 to 10 minutes. Triplicate 12-lead ECGs will be performed at predose and 4 hours (± 10 minutes) for all postbaseline assessments.
- j. For subsequent cycles, triplicate 12-lead ECGs are to be performed on Day 1 of Cycle 2 only.
- k. Single 12-lead ECGs will be performed on Cycle 3 Day 1 and Day 1 of subsequent cycles.
- l. Clinical chemistry and hematology tests are to be performed on Day 15 of Cycles 2, 3, and 4 only. For Cycles ≥ 5 , the Day 15 visit can be replaced with a telephone call to assess AEs and concomitant medications.

C
C
I

- o. Tumor assessments include imaging (e.g., CT, MRI, x-ray, FDG-PET) and caliper measurements, as applicable.
- p. Tumor assessments are to be performed on Cycle 3 Day 1 (± 7 days) and approximately every 6 weeks thereafter (e.g., Cycle 5 Day 1 [± 7 days], Cycle 7 Day 1 [± 7 days], etc.).
- q. Tumor assessments are to be performed only if clinically indicated. Patients who discontinue the study for a reason other than disease progression should be encouraged to continue with tumor assessments every 8 weeks ± 1 week until disease progression as determined by the Investigator, withdrawal of consent, initiation of subsequent anticancer therapy, the patient is lost to follow-up, or death, whichever occurs first.

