CR	CR	No	CR	Normalization of tumor markers, tumor nodes < 10 mm
CR	Non-CR/Non-PD	No	PR	
CR	Not all evaluated	No	PR	
PR	Non-PD/ not all evaluated	No	PR	
SD	Non-PD/ not all evaluated	No	SD	Documented at least once ≥ 6 to 8 weeks from baseline
Not all evaluated	Non-PD	No	NE	
PD	Any	Any	PD	
Any	PD	Any	PD	
Any	Any	Yes	PD	
Nontarget lesions ONLY				
No Target	CR	No	CR	Normalization of tumor markers, tumor nodes < 10 mm
No Target	Non-CR/non-PD	No	Non-CR/non-PD	
No Target	Not all evaluated	No	NE	
No Target	Unequivocal PD	Any	PD	
No Target	Any	Yes	PD	

Note: Patients with a global deterioration of health status requiring discontinuation of treatment without objective evidence of disease progression at that time should be reported as “symptomatic deterioration”. This is a reason for stopping therapy, but is NOT objective PD. Every effort should be made to document the objective progression even after discontinuation of treatment.

For nonrandomized trials, where confirmation of response is required, best overall response can be interpreted as follows:

Table 2: Interpretation of Best Overall Response

Response: First Time Point	Subsequent Time Point	BEST Overall Response	Also Requires
CR	CR	CR	Normalization of tumor markers, tumor nodes < 10 mm
CR	PR	SD, PD or PR (see comment*)	
CR	SD	SD provided minimum criteria for SD duration met, otherwise, PD	
CR	PD	SD provided minimum criteria for SD duration met, otherwise, PD	
CR	NE	SD provided minimum criteria for SD duration met, otherwise NE	
PR	CR	PR	
PR	PR	PR	
PR	SD	SD	
PR	PD	SD provided minimum criteria for SD duration met, otherwise, PD	
PR	NE	SD provided minimum criteria for SD duration met, otherwise NE	
NE	NE	NE	

CR = complete response; NE = not evaluable; PD = progressive disease; PR = partial response; SD = stable disease

* may consider PR providing initial “CR” likely PR on subsequent review – then original CR should be corrected. Recurrence of lesion after true CR is PD.

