1.4 Methods of Measurement

The same method of assessment and the same technique should be used to characterize each identified and reported lesion at baseline and during follow-up. Assessments should be identified on a calendar schedule and should not be affected by delays in therapy, which may be treatment-arm dependent. While on study, all lesions recorded at baseline should have their actual measurements recorded at each subsequent evaluation, even when very small (e.g., 2 mm). If it is the opinion of the radiologist that the lesion has likely disappeared, the measurement should be recorded as 0 mm. If the lesion is believed to be present and is faintly seen but too small to measure, a default value of 5 mm should be assigned. For lesions which fragment/split add together the longest diameters of the fragmented portions; for lesions which coalesce, measure the maximal longest diameter for the “merged lesion”.

Clinical lesions: Clinical lesions will only be considered measurable when they are superficial and ≥ 10 mm diameter as assessed using calipers (e.g., skin nodules). For the case of skin lesions, documentation by color photography including a ruler to estimate the size of the lesion is suggested. If feasible, imaging is preferred.

Chest X-ray: Chest CT is preferred over chest X-ray, particularly when progression is an important endpoint, since CT is more sensitive than X-ray, particularly in identifying new lesions. However, lesions > 20 mm on chest X-ray may be considered measurable if they are clearly defined and surrounded by aerated lung.

CT, MRI: CT is the best currently available and reproducible method to measure lesions selected for response assessment. This guideline has defined measurability of lesions on CT scan based on the assumption that CT slice thickness is 5 mm or less. When CT scans have slice thickness greater than 5 mm, the minimum size for a measurable lesion should be twice the slice thickness. MRI is also acceptable in certain situations (e.g., for body scans). While PET scans are not considered adequate to measure lesions, positron emission tomography-computerized tomography [PET-CT] scans may be used providing that the measures are obtained from the CT scan and the CT scan is of identical diagnostic quality to a diagnostic CT (with intravenous [iv] and oral contrast).

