#### 7.5.1 Objective Response Rate

ORR is defined as the proportion of patients who have achieved a best overall response (BOR) of complete response (CR) or partial response (PR) as determined by Investigator review of radiographic disease assessments per RECIST v1.1. Both confirmed and unconfirmed ORR will be summarized, but the primary analysis will be based on confirmed responses.

The BOR is defined as the best response recorded from the study start date until progression and will be determined programmatically based on the Investigator’s assessment of tumor response at each time point per RECIST v1.1. Only tumor assessments performed before the start of any subsequent anticancer therapies and not later than 30 days after last dose of study drug will be considered in the assessment of best overall response. Clinical deterioration or clinical progression noted on the End of Treatment Disposition eCRF will not be considered as documented disease progression for the purposes of the ORR calculation.

The confirmed BOR for each patient is determined from the sequence of overall timepoint (lesion) responses according to the following rules below:

CR = at least two determinations of CR at least 4 weeks apart before progression, where confirmation required, or one determination of CR prior to progression, where confirmation not required.

PR = at least two determinations of PR or better at least 4 weeks apart before progression (and not qualifying for a CR), where confirmation required, or one determination of PR prior to progression, where confirmation not required.

SD = an assessment of SD or better > 6 weeks after start of treatment (and not qualifying for PD, PR or CR).

PD = progression  $\leq$  9 weeks after start of treatment (and not qualifying for CR, PR, or SD).

NE (Not Evaluable) = all other cases (i.e. not qualifying for confirmed CR or PR and without SD after more than 6 weeks or early progression within the first 9 weeks).

Patients with confirmed best overall response 'Not Evaluable' will be summarized by reason for having unknown status. The following reasons will be used:

- No baseline assessment
- No adequate post-baseline assessment
- All post-baseline assessments have overall response of "NE"
- New anticancer therapy started before first post-baseline assessment
- SD occurred  $\leq$  6 weeks after the start of treatment

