- Progression >9 weeks after the start of treatment (i.e. tumor assessment of PD was >9 weeks after start of treatment and there was no tumor assessment in between)

Special (and rare) cases where BOR is 'Not evaluable' due to both SD occurring  $\leq$  6 weeks after start of treatment and progression > 9 weeks after the start of treatment will be classified as "SD occurred  $\leq$  6 weeks after the start of treatment".

The ORR will be calculated with an exact two-sided 95% CI. The 95% CI will be derived using the Clopper-Pearson exact binomial CI method. In addition, the number and percentage of patients in each BOR category (i.e., CR, PR, stable disease (SD), progressive disease (PD), and Not Evaluable) will be summarized.

A figure for duration of exposure and best overall response (confirmed) will be created.

A waterfall plot will be created to show the best percentage change from the baseline in the sum of longest diameters. Patients with baseline and at least one post-baseline tumor assessment will be included in the waterfall plot.

Individual lesion measurements and overall response assessments per RECIST v1.1 will be listed by patient and assessment date.

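### SAP 7.5.1 sets the SD cut-off on the nominal first-scan day and ends the PD limit before the second scan, so some patients scanned on schedule become Not Evaluable

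*SAP*

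**What the plan says.** **Scan timing.** Protocol Section 8.7, Table 11, footnote p: "Tumor assessments are to be performed on Cycle 3 Day 1 (± 7 days) and approximately every 6 weeks thereafter". Protocol 6.3 fixes the cycle length: "cycles are defined as 21 days and pembrolizumab should be administered Q3W". Protocol Appendix 5, Section 1.4, ties scans to the calendar: "Assessments should be identified on a calendar schedule and should not be affected by delays in therapy".

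**Response categories.** Under SAP 7.5.1 a patient without a confirmed response is SD given "an assessment of SD or better > 6 weeks after start of treatment", PD if progression came at or before week 9, and otherwise NE, which the SAP explains as "without SD after more than 6 weeks or early progression within the first 9 weeks". The listed NE reasons include SD seen at or before 6 weeks and "Progression >9 weeks after the start of treatment". Where both apply, the SAP uses the first reason and describes the case as special and rare. SAP 7.5.5 reuses this derivation for the immune-related best response.

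**The protocol's own rule.** Appendix 5, Table 1, asks for SD to be "Documented at least once ≥ 6 to 8 weeks from baseline". Appendix 5, Table 2, makes a PR followed by PD count as SD if the SD minimum was met, and as PD if it was not. SAP 6.0 declares no departure from the protocol's analyses.

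**The concern.** The SD cut-off is a strict inequality at 6 weeks, which is the day on which the first scan is nominally due, and it makes no allowance for the 7 days either side. The PD limit closes at 9 weeks, before the second scan can take place within its window. A patient who is stable at a slightly early first scan and progresses at the second falls between the two rules. That patient has two on-schedule, readable scans and a documented progression, and is still reported as not evaluable.

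The category then turns on which side of one calendar day the scan fell, not on the tumour. NE is normally read as missing or inadequate assessment. Placing assessed patients there makes follow-up look less complete than it was and understates SD or PD. In cohorts of 23 and 29 patients, or 9 and 15 if a cohort stops at Stage 1, a few such patients would visibly change the table.

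**Working it through.** The plan gives no figure for how often this happens, only the description of the case as rare, so there is no number to reproduce. The check is a day count.

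**1. Scan windows, in days elapsed since treatment start.**
- Scan 1, Cycle 3 Day 1: 2 × 21 = 42; window 42 ± 7 = 35 to 49 (5 to 7 weeks).
- Scan 2, Cycle 5 Day 1: 4 × 21 = 84; window 84 ± 7 = 77 to 91 (11 to 13 weeks).

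**2. SAP cuts.** SD: more than 6 × 7 = 42 days. PD: at most 9 × 7 = 63 days.

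**3. Which scans the PD limit reaches.** The latest scan 1 is at 49 days, inside 63, so PD at scan 1 is always classed as PD. The earliest scan 2 is at 77 days, beyond 63, so PD first seen at scan 2 never is.

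**4. Consequence.** For SD or an unconfirmed PR at scan 1 followed by PD at scan 2, the category depends only on the date of scan 1: SD if it passes the 42-day cut, NE if it does not.

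**5. Window days that fail.** SAP 7.5.1 does not say how to count weeks after start. SAP 7.1.6 (study day) and 7.1.7 (durations) both add 1 day.
- Elapsed days: 35 to 42 fail, 8 of 15 = 53%.
- Date difference plus 1: counted days 36 to 42 fail, 7 of 15 = 47%.

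The two conventions differ only for a scan done exactly on Cycle 3 Day 1, which fails at 42 elapsed days and passes as Day 43.

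**6. From window days to patients.** This needs the spread of actual scan dates, which the documents do not give. Under assumed spreads, the share of patients with this pattern who become NE is:

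| Assumed scan-1 dates | Elapsed days | Plus 1 |
|---|---|---|
| Even over ± 7 days | 53% | 47% |
| Triangular, peak on nominal day | 56% | 44% |
| Normal, SD 3 days | 57% | 43% |
| Even over ± 2 days | 60% | 40% |
| 7 days early to nominal day | 100% | 88% |
| Nominal day to 7 days late | 13% | 0% |
| All on nominal day | 100% | 0% |

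**7. Against Appendix 5.** Take a baseline scan 14 days before the first dose, an unconfirmed PR 38 days after it, and PD at 84 days. The PR is 14 + 38 = 52 days (7.4 weeks) from baseline. Appendix 5 gives SD if its minimum is read as 6 weeks and PD if it is read as 8 weeks. The SAP gives NE, because 38 is not above 42. None of the SAP's listed NE reasons plainly describes this patient, since the early finding was a PR and not SD. Table 2 has no row for SD then PD, so the direct conflict concerns an initial response that is not confirmed; applying it to SD then PD is by analogy.

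**8. What does not move.** SD, PD and NE are all non-responses in the full analysis set, so confirmed ORR is the same whichever applies. The Simon rules count responders only. PFS (SAP 7.5.3) uses its own event and censoring dates. Duration of response covers confirmed responders only.

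**The case against.** The best defence is that this is a pre-specified minimum-duration convention, openly applied. The SAP foresaw SD followed by late PD, gave it a reason code, tabulates NE by reason, and lists every dated response, so a reader could recover these patients. Under either day count that the SAP defines, a scan on the exact nominal day passes, so only early scans fail. Disease control rate appears only in the SAP's abbreviation list, not among the visible endpoints. A shorter SD minimum would itself depart from the protocol: a scan 35 days after start is less than 6 weeks from baseline when the baseline scan was done within the week before dosing.

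Much of this stands. The SAP did not overlook the pattern, the primary endpoint is untouched, and a 35-day cut has a price. Three points remain. The schedule gives no ground for calling the case rare when about half of the permitted days fail. SAP 7.5.1 does not say that it adopts the plus-1 count. And an unconfirmed PR followed by PD cannot be NE under Appendix 5, while SAP 6.0 declares no change.

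A reader might go further and infer that about half of patients with this pattern will be misclassified, or put a patient count on it. The documents do not support either. About half is a share of window days; it becomes a share of patients only if scan dates are spread roughly evenly around the nominal day. A count also needs the proportion with SD or unconfirmed PR and then PD. If that were 20% to 40% (an assumption), the affected part of a cohort could be anything from 0% to 40%. Nor does the PD limit misfit the first scan; it covers that scan and ends before the second.

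**Conclusion.** The gap is real and follows from the stated rules. SD or an unconfirmed PR at an in-window first scan on or before the cut, followed by PD at the second scan, is classed NE although both scans were done on schedule. Seven of 15 permitted days lead there under the plus-1 count and 8 of 15 under elapsed days. The share of patients with this pattern who are affected is unknown, with a full range of 0% to 100%.

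The distortion is confined to the SD, PD and NE split of the best-response and immune-related best-response tables, and to the figure showing confirmed best response. A reader who took this as a threat to ORR, the Simon decisions or PFS would be mistaken. It should be corrected before database lock because a written rule puts assessed patients in the wrong row of a specified table.

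The conclusion assumes that both scans fall in their windows with no other scan between them, and that scan 2 is admissible under SAP 7.5.1 (before any new anticancer therapy and within 30 days of the last dose). The comparison uses protocol Version 4. The SAP cites Version 5, which was not available for this check.

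**What to change.** In SAP 7.5.1, and for irSD through 7.5.5:

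1. State the day count used for weeks after start of treatment.
2. Set the SD minimum to allow for the scan window, for example at least 35 days after treatment start. All 15 window days then qualify and NE for this pattern falls to 0%. Changing only the strict inequality to at-least-6-weeks, on elapsed days, still leaves 7 of 15 days failing.
3. Class patients who miss the SD minimum and then have documented PD at the next scheduled scan as PD rather than NE, in line with Appendix 5, Table 2.
4. Reconcile the new minimum with the Appendix 5 range of 6 to 8 weeks from baseline, choosing one number and one starting point, and record the change in SAP 6.0.
5. Align the NE reasons with the new cut and remove the description of the case as special and rare.

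The cost is SAP wording and a small programming change. There is a small downside: a declared departure from the Appendix 5 SD minimum, and a slightly more lenient SD row.

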### 7.5.2 Duration of Response

DOR is defined as the time from the date of the first documented response (CR or PR) to the earliest date of disease progression, as determined by Investigator review of radiographic disease assessments per RECIST v1.1, or death due to any cause. If a patient with a CR or PR has neither progressed nor died at the time of the analysis cutoff or at the start of any new anticancer therapy, the patient will be censored at the date of last adequate tumor assessment. DOR will be calculated for patients who have achieved a confirmed overall response (i.e., CR or PR).

An estimate of the DOR survival function will be constructed using the Kaplan-Meier (product-limit) method (Kaplan & Meier, 1958) as implemented in PROC LIFETEST. The 25%, median, and 75% DOR (in months) will be summarized along with 95% CIs as calculated from the PROC LIFETEST output (using method of [Brookmeyer & Crowley, 1982]).

Frequency counts and percentages of patients with each event type (PD or death) and censoring reasons will be summarized. Censoring reasons are as follows:

- Ongoing in the study without an event
- No baseline assessment
- No post-baseline assessment
- New anticancer therapy was given
- Progression after 2 or more missed assessments
- Death after 2 or more missed assessments
- Adequate assessment no longer available
- Withdrawal of consent
- Lost to follow-up

A Kaplan-Meier plot of the survival function will be provided as well.

Duration of response will be listed.

### 7.5.3 Progression-free Survival

PFS is defined as the time from the date of first dose of study drug to the earliest date of disease progression, as determined by Investigator review of radiographic disease assessments per RECIST v1.1, or death due to any cause.

If a patient has not had a PFS event at the time of the analysis cutoff or at the start of any new anticancer therapy, PFS will be censored at the date of last adequate tumor assessment. If a PFS event is observed after more than one missing or inadequate tumor assessment, PFS will be

censored at the last adequate tumor assessment. If a PFS event is observed after a single missing or non-adequate tumor assessment, the actual date of event will be used. Patients who do not have baseline or post-baseline tumor assessments will be censored at the study start date.

The last adequate tumor assessment is defined as a tumor assessment result that is not “NE”, “ND”, “NA” or missing.

The survival distribution function for PFS will be estimated using the Kaplan-Meier (KM) method as described for DOR in Section 7.5.2. The PFS rate at 2, 4 and 6 months will be estimated with corresponding two-sided 95% CIs.

Frequency counts and percentages of patients with each event type (PD or death) and censoring reasons will be summarized as described in Section 7.5.2.

In addition, time to progression/censoring, event and censoring reasons will be listed.

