11.1.2 Efficacy Analysis

11.1.2.1 Efficacy Analyses Using Response Criteria in Solid Tumors

Objective response using RECIST will be defined as CR + PR, as determined by the Investigator. Objective response rate is defined as the proportion of patients who achieve an objective response. The objective response rate along with exact 95% CIs ([Clopper and Pearson 1934](#)) will be reported.

Duration of response will be calculated for patients who achieve an objective response (i.e., CR or PR, as determined by the Investigator) and is defined as the time from the first documented response to the date of documented progression or death after achieving a response. If a patient has not had a PFS event at the time of the analysis cutoff or at the start of any new antineoplastic therapy, duration of response is censored at the date of last adequate tumor assessment. The survival distribution function for duration of response will be estimated using the Kaplan-Meier method.

Progression-free survival is defined as the time from the start of treatment to the time of first documented progression or death, whichever occurs first. If a patient has not had a PFS event at the time of the analysis cut-off or at the start of any new anti-neoplastic therapy, PFS is censored at the date of last adequate tumor assessment. The survival distribution function for PFS will be estimated using the Kaplan-Meier method.

Overall survival is defined as the time from the start of treatment to the date of death due to any cause. If a death has not been observed by the date of the analysis cutoff, OS will be censored at

the date of last contact. The survival distribution function for OS will be estimated using the Kaplan-Meier method.

If the patient achieves a CR or PR and progression has not been documented and the patient is still alive at the time of analysis, the duration of response is censored on the date of the last tumor assessment.

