## 1.0 INTRODUCTION

This document describes the statistical analyses and data presentations to be performed for the clinical protocol ARRAY-382-201 entitled “A Phase 1b/2 Study of ARRY-382 in Combination with Pembrolizumab, a Programmed Cell Death Receptor 1 (PD-1) Antibody, for the Treatment of Patients with Advanced Solid Tumors”.

This statistical analysis plan (SAP) should be read in conjunction with the study protocol and electronic case report forms (eCRFs). This document has been developed using the protocol Version 5 dated 02 January 2019 and eCRFs dated 13 June 2018. Any further changes to the protocol or eCRFs may necessitate updates to the SAP.

This SAP provides a comprehensive and detailed description of the strategy, rationale and statistical techniques to be used to assess the safety, efficacy, pharmacokinetics (PK) CCI analyses in adult patients with selected advanced solid tumors (Part A/Phase 1b); in adult patients with advanced solid tumors that have progressed on prior PD-1/PD-L1 inhibitors, in adult patients with platinum-resistant ovarian cancer (prOVCA) and in patients with pancreatic ductal adenocarcinoma (PDA) (Phase 2). The purpose of this SAP is to ensure the credibility of the study findings by specifying the statistical approaches for the final analysis of study data. This SAP will be finalized and signed prior to the clinical database lock.

Statistical analyses detailed in this SAP will be conducted using SAS®, Version 9.4 or higher (SAS Institute, Inc., Cary, NC USA). Noncompartmental PK analyses will be performed with Phoenix® WinNonlin® Version 8.0 or higher (Certara USA, Inc., Princeton, NJ). Original sample size calculations for Phase 2 were conducted using R, Version 3.4.3.

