## 6.0 CHANGES FROM THE STUDY PROTOCOL

There are no changes from the statistical analyses described in the study protocol at this time.

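### SAP 7.5.3 counts death as a PFS event, but its start-date censoring sentence makes no exception for patients who died, so early deaths without a scan can be read as zero-time censorings in PFS and irPFS

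*SAP*

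**What the plan says.** SAP 7.5.3 measures PFS from the first dose to radiographic progression or death from any cause, whichever is earlier. It then gives four censoring rules in sequence:

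1. A patient with no PFS event at the analysis cutoff or "at the start of any new anticancer therapy" is censored at the last adequate tumor assessment.
2. An event after more than one missing or inadequate assessment is censored at the last adequate assessment.
3. "If a PFS event is observed after a single missing or non-adequate tumor assessment, the actual date of event will be used".
4. "Patients who do not have baseline or post-baseline tumor assessments will be censored at the study start date".

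No order of precedence is stated. For censoring reasons, 7.5.3 points back to the list in SAP 7.5.2, which contains "No post-baseline assessment" and, separately, "Death after 2 or more missed assessments". SAP 7.5.6 defines irPFS with death as an event and applies the 7.5.3 censoring rules.

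Protocol 11.1.2.1 also counts death as a PFS event. Its DOR rule opens with "If a patient has not had a PFS event at the time of the analysis cutoff", its PFS rule sets the same condition, and neither contains a start-date rule. SAP 6.0 says: "There are no changes from the statistical analyses described in the study protocol at this time". The protocol supplied is Version 4, whereas SAP 1.0 says: "This document has been developed using the protocol Version 5 dated 02 January 2019". The conflict lies within the SAP and does not depend on the protocol version.

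**The concern.** Rule 4 is triggered by the absence of scans, not by the absence of an event. A patient who dies before any post-baseline scan has had a PFS event by definition, yet also meets the wording of rule 4. Two programmers could code this differently and obtain different curves from the same data.

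The patients concerned have the worst outcomes in the cohort. Censoring them at time zero treats their deaths as uninformative and can only raise the estimate. The outputs exposed are the planned 2-, 4- and 6-month PFS rates, the PFS median and the corresponding irPFS results. These patients cannot drop out through the population definition, because the full analysis set in SAP 5.3 is everyone who received at least one dose and is used for all efficacy analyses.

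Rule 4 also names a study start date that the SAP does not define. SAP 7.1.5 defines a treatment start date.

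**Working it through.** The plan gives no figure to reproduce here. The check sets the rules against the scan schedule and then works through the Kaplan-Meier arithmetic.

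**Schedule.** Cycles are 21 days (Protocol 6.3). Scans fall on Day 1 of Cycles 3, 5, 7 and so on, each ±7 days (Protocol Table 11).
- First scan: 1 + 2×21 = Day 43, window Day 36 to 50.
- Second scan: 1 + 4×21 = Day 85, window Day 78 to 92.

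**Rules applied to a patient who dies with no post-baseline scan, no documented progression and no new therapy.**

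| Time of death | Scans missed | Definition and rules 1 to 3 | Rule 4, literal | Conflict |
|---|---|---|---|---|
| Before the first scan is due | 0 | Event at death | Censored at start | Yes, with the PFS definition |
| After the first is missed, before the second is missed | 1 | Event at death (rule 3) | Censored at start | Yes, with the adjacent sentence |
| After two are missed | 2 or more | Censored (rule 2) | Censored at start | No |

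Rule 4 could be read as covering only patients who lack both a baseline and a post-baseline scan. The 7.5.2 list names the two as separate reasons, which indicates that either one is enough.

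**Effect on the curve.** Let N patients include k deaths of the first two kinds. Let p further patients have an event by a later time t, and assume no other censoring before t.
- Deaths counted as events: S(t) = (N-k-p)/N
- Deaths censored at start: S(t) = (N-k-p)/(N-k)
- Ratio: N/(N-k), which exceeds 1 whenever k is at least 1

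Taking a value of 50% with deaths counted as events, the literal reading gives 50% × N/(N-k):

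| N (planned cohort) | k=1 | k=2 | k=3 |
|---|---|---|---|
| 20 (PD-1/PD-L1 refractory) | 52.6% | 55.6% | 58.8% |
| 23 (prOVCA) | 52.3% | 54.8% | 57.5% |
| 29 (PDA) | 51.8% | 53.7% | 55.8% |

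A count example: N=29, k=3 deaths before the first scan, and 13 of the other 26 patients progressing at that scan. Two months is 2 × 30.4375 = 60.9 days, after the first scan. The 2-month rate is 13/29 = 44.8% with deaths as events and 13/26 = 50.0% with start-date censoring.

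The values of k are assumed. The documents give no rate of death before a first scan.

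**The case against.** The strongest reply is that rule 4 was never meant for patients who died. Rule 1 censors event-free patients at the last adequate assessment. A patient with no scan has no such date, so rule 4 naturally supplies one. The condition in Protocol 11.1.2.1, the no-change statement in SAP 6.0 and the single death-related censoring reason, which requires two or more missed assessments, all point the same way. This largely stands: the fallback reading is the more probable intent. It does not settle the matter, because rule 4 does not state the limit, no other text supplies it, and the reason for having no post-baseline scan also lacks a death exception.

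A second reply is that little turns on it. No PFS hypothesis test is planned. At N=23 and 50%, a simple binomial 95% half-width is 1.96 × √(0.5×0.5/23) = 20.4 points, against shifts of 2.3 to 7.5 points in the table. Events and censoring reasons are tabulated and listed, so an affected patient would be visible, though only once the analysis had been run. This also stands, and it is why the point is minor.

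Third, the study start date is loose wording that SAP 7.5.1 also uses. Since PFS runs from first dose, the intended date can be inferred. That is fair, but the defined term costs nothing.

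**Conclusion.** Wrong as written; minor, and confined to secondary descriptive endpoints. Rule 4 contradicts rule 3 for a death after exactly one missed scan, and contradicts the PFS definition for a death before the first scan. If it is followed literally, PFS and irPFS are biased upward by the factor N/(N-k), assuming no other early censoring. The direction is certain; the size is not, because k is unknown. ORR, both Simon decisions and OS are untouched.

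Two stronger readings go beyond the documents. A reader might infer that the sponsor plans to censor early deaths; the surrounding text favours the fallback reading. A reader might also try to predict k from the median PFS and OS that Protocol 2.1.4 quotes for ovarian cancer. Those medians come from 26 PD-L1-positive patients given pembrolizumab alone. The result would also depend on whether progression can be documented before the first scheduled scan and on how often early death follows progression, neither of which the documents settle.

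**What to change.** Replace rule 4 in SAP 7.5.3 with:

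> A patient without a PFS event (neither documented progression nor death) who has no baseline or no adequate post-baseline tumor assessment is censored at the treatment start date. For patients with an event, the rules above on more than one missing or inadequate assessment and on new anticancer therapy continue to apply; where they call for censoring at the last adequate assessment and no adequate post-baseline assessment exists, the treatment start date is used.

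Apply the same text to irPFS under SAP 7.5.6. Limit the two censoring reasons for a missing baseline or missing post-baseline assessment to patients without an event. Conditioning on any event, not only on death, keeps a documented progression at its own date in a patient without a baseline scan.

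Do not add a count of missed scans on the 8-weekly schedule after treatment stops. Protocol 8.5 only encourages those scans and calls for them when clinically indicated, so a missed one is not well defined.

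The cost is two SAP sentences in place of one, the matching program line and two censoring categories. No new data are needed. Protocol 11.1 reserves protocol amendments for major changes to a primary endpoint definition or analysis, so none is called for. The downside is that reported PFS and irPFS may be slightly less favourable than under the literal rule.
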